#### 11.3.3 Timed Up & Go Test

This test will assess the extent of the subject's composite mobility, including standing up, walking, repositioning the body, and balancing.

The time required for the subject to stand up from a sitting position on a table (chair), walk to a cone placed 3 m ahead as quickly as possible, and then return to the table will be evaluated.

With the table stabilized against a wall (0-m point will be the front center of the table) and the back of the subject leaning against a backrest (wall) at the start, the time from the start call to the subject's return with his back against the backrest after going around the cone will be measured with a stopwatch (unit: second, time measured to 2 decimal places). There is no time restriction for the test. For details of the preparation, implementation procedures, important points, safety considerations, etc., the evaluation procedure will be followed.

## 11.3.4 Timed 10-m walk/run test

The time required for the subject to run or walk as quickly as possible a 10 m-wide passage with marks affixed on the floor will be evaluated. The test will be performed using more than a specified width of flat straight line (a quiet indoor hallway, etc.). 10 meters will be measured with a tape measure, and marks affixed to both the 0-m (start line) and 10-m (goal line) ends. With the subject in a standing position just behind the start line at the start, the time from the start call to the subject's leg passing the goal line will be measured with a stopwatch (unit: second, time measured to 2 decimal places). There is no time restriction

for the test. For details of the preparation, implementation procedures, important points, safety considerations, etc., the evaluation procedure will be followed.

## 11.4 Evaluation of Muscle Volume

#### 11.4.1 Skeletal Muscle CT

To estimate the skeletal muscle volume using muscle CT, muscle volume index (MVI), %MVI, and net muscle volume\_CT (nMV\_CT), which indicate the cross-sectional area of the middle of a muscle, muscle survival rate (proportion), and CT-based skeletal muscle volume in a given section, respectively, will be used. MVI, which is the cross-sectional area of the middle of a muscle (unit: cm^2), will be measured in both legs. As %MVI, which is intended to estimate the skeletal muscle volume based on the CT values in the cross-section of a middle thigh, the muscle survival rate (proportion of actual muscle in the cross-section of the original muscle, unit: %) will be measured in only 1 leg (right leg in principle) using an estimator. In addition, nMV\_CT, which is the skeletal muscle volume in a given section of the middle thigh (unit: cm^3), will be measured in both legs using an estimator. All parameters will be measured in the lower leg as well as the middle thigh. The obtained CT images (DICOM data) will be submitted to the sponsor by each study site. Based on the data submitted to the sponsor, the images will be centrally evaluated by the muscle volume evaluator. For details of the measurement method, measured site, and evaluation method, the evaluation procedure will be followed.

## 11.4.2 BIA

The skeletal muscle volume (unit: kg, 2 decimal places) at the left and right sites (in each limb) will be measured by BIA (TANITA body composition monitor: Inner Scan® 50V model BC-622). Since the lower age limit for skeletal muscle measurement is 6, subjects aged 5 at the baseline evaluation will be handled as those aged 6 for the measurement. For all subjects, the age at the baseline evaluation will be used for the measurement throughout the study period. For details of the measurement method and evaluation method, the evaluation procedure will be followed.

#### **11.5 Lean Body Mass**

Lean body mass (kg) will be calculated by deducting the body fat that is calculated from the body fat percentage measured by BIA (TANITA body composition monitor: Inner Scan® 50 V model BC-622) from the body weight. The lean body mass calculation formula shall be as follows: body weight (kg, 1 decimal place) - [body weight (kg, 1 decimal place) × body fat percentage (%, 1 decimal place)] = lean body mass (kg, the value shall be rounded to 1 decimal place).

#### **11.6 Evaluation of Muscle Strength**

#### **11.6.1** Quantitative Muscle Strength Assessments

Quantitative muscle strength assessments will be performed using a hand-held dynamometer (Nihon Medix microFET2TM; manual muscle measurement/evaluation equipment will be specified). Muscle strength for hip flexion/extension, knee flexion/extension, ankle extension/flexion will be evaluated [measurement unit: newton (N), 1 decimal place]. For details of the preparation, implementation procedures, important points, safety considerations, etc., the evaluation procedure will be followed.

## **11.7 Other Efficacy Evaluations**

## 11.7.1 Serum CK Concentration

Since CK, a muscle-specific enzyme, is known to leak out of muscle cells of a damaged muscle tissue and is released into the blood, plasma CK concentration may reflect the extent of muscle damage. For this purpose, serum CK concentration will be measured and evaluated using blood samples collected for biochemistry. Only the serum CK concentration measured during the hospitalization period will be used for the efficacy evaluation. The rationale is described in Section 14.1.

# 11.7.2 Pulmonary Function Test

Noninvasive vital capacity measurement will be performed using a spirometer, and the measured values of VC (unit: L), FVC (unit: L), FEV1.0 (forced expiratory volume in first second, unit: L), and FEV1.0% (percent ratio of FEV1.0 to FVC; FEV1/FVC, unit: %) will be evaluated.

# 12. Safety Evaluation

## 12.1 Adverse Events

## 12.1.1 Definition of Adverse Event

An adverse event is defined as any unfavorable medical event that occurs in a subject participating in the study, regardless of whether it is considered related to the investigational product.

A diagnosis will be recorded as an adverse event wherever possible. If no definite diagnosis can be established, signs or symptoms will be recorded.

Symptoms associated with DMD or concurrent illnesses and abnormal laboratory or other test findings that have been present since before the study initiation will not be assessed as adverse events. However, any new symptoms or worsening of concurrent illnesses will be assessed as adverse events.

All clinically or medically significant abnormal test values will be reported as adverse events. Symptoms derived from a diagnosis already reported as an adverse event by the investigator or subinvestigator will not be assessed as adverse events.

Abnormal laboratory test values assessed as adverse events are:

- those requiring medical treatment
- those requiring prolonged administration, discontinuation, or dose reduction of the investigational product
- those deemed medically significant by the investigator or subinvestigator for any other reason

For report on the follow-up of pregnancy of the subject's partner or definition and report of medication errors, misuses, and drug interactions, refer to Section 12.7, "Other Information."

Adverse events will be evaluated from the time of informed consent, while those developed or worsened after start of investigational product administration will be collected on the CRFs. For any other details of recording, the "Instructions for Completing the CRFs and Making Changes or Corrections to the CRFs" will be referred to.

For each efficacy evaluation parameter (serum CK concentration will be applicable only during the hospitalization period), any clinically or medically significant change will not be assessed as adverse event.

## 12.1.2 Severity of Adverse Events

One of the following severities of adverse events will be selected and evaluated [semicolon (;) means "or"]:

Mild:

Mild; no symptom or mild symptom; only clinical or test finding; requiring no treatment Moderate:

Moderate; requiring minimum/local/non-invasive treatment; limiting age-appropriate activities of daily living except for self-care\*

Severe:

Severe or medically significant, but not immediately life-threatening; requiring hospitalization or prolongation of existing hospitalization; disability; limiting self-care activities.\*\* An event leading to

life-threatening consequences or requiring emergency intervention, or death due to adverse event is also assessed as severe.

\* "Activities of daily living except for self-care" refers to meal preparation, shopping for daily goods and clothing, use of a telephone, financial management, etc.

\*\* "Self-care activities" refers to bathing, dressing/undressing, food intake, use of a bathroom, and oral drug intake without being bedridden.

# 12.1.3 Causal Relationship to the Investigational Product

The causal relationship of an adverse event to the investigational product will be assessed as one of 2 categories as described below, based on various factors (e.g., the subject's condition, previous medical history, concomitant medications, temporal association between investigational product administration and the onset of the adverse event).

- (1) There is a reasonable possibility: The onset of the adverse event is temporally associated with investigational product administration, and meets any of the following conditions:
  - The event resolved by dose suspension: The event improved or resolved after (temporary or permanent) suspension of investigational product administration.
  - The event recurred after dose resumption: The event recurred after resumption of investigational product administration.
  - The event cannot be explained reasonably based on the subject's clinical symptoms and/or therapies other than the investigational product.
  - The event is known to occur, although scarcely, after medication (e.g., angioedema, Stevens-Johnson syndrome).
- (2) There is no reasonable possibility: There is no evidence of causal relationship of the adverse event to the investigational product.

The adverse event is assessed to have no reasonable possibility under the following conditions:

- The adverse event occurred before administration of the investigational product.
- There is no reasonable possibility that the administration of the investigational product caused the adverse event.
- The onset of the adverse event is not temporally associated with investigational product administration, and may be due to concurrent illness, concomitant medications, clinical symptoms, etc., of the subject

# 12.1.4 Definition of Adverse Drug Reaction

An adverse event (including an abnormal laboratory value) assessed by the investigator, subinvestigator, or the sponsor as reasonably related to the investigational product will be regarded as an adverse drug reaction in this study.

# 12.1.5 Outcome of Adverse Events

(1) Resolved: The symptom or finding resolved or returned to the baseline level.

- (2) Resolving: The symptom or finding nearly resolved or returned to the baseline level.
- (3) Not resolved: The symptom or finding is unchanged with no resolve.
- (4) Resolved with sequelae: The symptom resolved, but with evidence of adverse event-related dysfunction interfering with daily life.
- (5) Death: The subject died due to the adverse event.

# 12.1.6 Reporting of Adverse Events

Adverse events will be reported from the day of informed consent by the subject's legal representative or the subject to the end of the evaluation in the follow-up test described in Section 5.2.5. All adverse events will be recorded in the source documents.

Any adverse event determined to be related to the investigational product by the investigator or subinvestigator will be collected, regardless of the time of onset.

# 12.1.7 Follow-up of Adverse Events

If an adverse event occurs, the investigator or subinvestigator will take appropriate measures immediately and follow up the event until it is confirmed to have resolved or to be resolving. If follow-up of an adverse event cannot be continued for any of the reasons listed below, the reason will be described on the CRF.

- The causal relationship between the event and the investigational product cannot be determined due to another treatment given to the subject.
- Further follow-up is impossible, due to hospital change, etc.
- The subject and his legal representative refuse follow-up.
- The subject died.
- The adverse event is not resolved or resolving, but the investigator or subinvestigator concludes that the event is stable or there will be no further improvement.

# 12.2 Serious Adverse Events

## 12.2.1 Definition of Serious Adverse Event

A serious adverse event is defined, regardless of the dosage of the investigational product, as any adverse event that:

- (a) Results in death.
- (b) Is life-threatening.

Note: "Life-threatening" serious adverse event refers to an event in which the subject was at risk of death at the time of the event; it does not refer to an event that hypothetically might have caused death if it were more severe.

- (c) Requires hospitalization or prolongation of existing hospitalization for the treatment. However, the following will not be assessed as hospitalization in the evaluation of seriousness of adverse events:
  - Visit to the emergency department less than 24 hr after the event
  - Previously scheduled hospitalization
  - Hospitalization to receive tests related to the study
- (d) Results in persistent or significant disability/incapacity.

- (e) Results in congenital anomaly/birth defect. (where exposure to the investigational product immediately before or during pregnancy adversely affected the fetus)
- (f) Is an important medical event.

Note: This refers to an important medical event that is not immediately life-threatening or fatal, or does not result in hospitalization, but may expose the subject to danger or require intervention or treatment to prevent the results described in above (a) to (e).

This includes, for instance, allergic bronchospasm requiring intensive care at the emergency department, home, etc.; blood disorder or spasm that does not result in hospitalization; and drug dependence or abuse.

## 12.2.2 Reporting of Serious Adverse Events

Serious adverse events will be reported to the sponsor within 24 hr from the time the investigator or subinvestigator first becomes aware of the event. The causal relationship and seriousness shall be carefully determined, and the comprehensive information obtained at the first reporting of the event (e.g., clinical course, previous medical history, concomitant medications) reported.

After the first reporting of the serious adverse event to the sponsor, any significant additional information on the event (diagnosis, outcome, evaluation of the causal relationship, certain test results, etc.) will be reported whenever it is obtained.

The investigator will respond to any request for further necessary information by the sponsor, the head of the study site, or IRB.

All serious adverse events that occur during the study period will be reported to the sponsor.

Any serious adverse event (including death) that occurs outside the study period will be reported to the sponsor only if the relationship of the event to the investigational product is indicated by the investigator.

[Emergency contact (sponsor)]

Clinical Development Division, Taiho Pharmaceutical Co., Ltd.

(from 8:40 am to 5:30 pm, except weekends, holidays, and December 29 to January 4)

After office hours, contact the product leader or clinical team leader.

For contact information of the product leader and clinical team leader, see the attachment.

## 12.2.3 Follow-up of Serious Adverse Events

If a serious adverse event occurs, the investigator or subinvestigator will take appropriate measures and follow up the event until it is confirmed to have resolved or to be resolving. If follow-up of a serious adverse event cannot be continued for any of the reasons listed below, the reason will be recorded on the Serious Adverse Event Report and CRF.

- The causal relationship between the event and the investigational product cannot be determined due to another treatment given to the subject.
- Further follow-up is impossible, due to hospital change, etc.
- The subject and his legal representative refuse follow-up.

- The subject died.
- The serious adverse event is not resolved or resolving, but the investigator or subinvestigator concludes that the event is stable or there will be no further improvement.

#### 12.3 Worsening of Underlying Disease

Worsening of underlying disease will not be used as an adverse event term. For worsening of underlying disease, the associated signs, symptoms, or concurrent illnesses will be reported as adverse events, or as serious adverse events if any of the seriousness criteria are met. In any case, the relationship of the signs, symptoms, or concurrent illnesses to the worsening of underlying disease will be clarified.

### 12.4 Reporting of Death

Any death, including that due to worsening of underlying disease, during the study period will be reported to the sponsor within 24 hr from the time the investigator or subinvestigator first becomes aware of the event, following the same procedure as for serious adverse events.

Since death is an outcome of an adverse event, it will not be used as an adverse event or serious adverse event term.

#### 12.5 Adverse Events of Special Interest

## 12.5.1 Definition of Adverse Events of Special Interest

Adverse events of special interest will not be defined in this study.

### 12.6 Predictability

Since no serious adverse drug reactions have occurred with TAS-205, all adverse events that occur in this study will be handled as "unexpected" events.

#### **12.7** Other Information

### 12.7.1 Follow-up of Pregnancy

Any pregnancy or outcome of the pregnancy of a subject's partner during participation in this study that is found by the investigator or subinvestigator will be reported promptly.

The information on pregnancy will be recorded on a pregnancy evaluation sheet and reported to the sponsor via e-mail or fax.

Any new information and/or correction of the previous information obtained after submission of the pregnancy evaluation sheet will be newly recorded on another pregnancy evaluation sheet and reported to the sponsor via e-mail or fax.

The investigator or subinvestigator will follow up the pregnancy of the subject's partner and report the outcome. Outcome of the pregnancy such as stillbirth, congenital disorder/birth defect, or serious maternal event, will be reported to the sponsor as a serious adverse event. In addition, the investigator or subinvestigator will follow up the child and convey any information indicative of involvement of the investigational product to the sponsor even after study completion.

## 12.7.2 Medication Errors

In this study, a medication error is defined as any unintended error, for instance, in the prescription, dispensing, or administration of the investigational product, that occurs under the management of a health

66

care provider or a subject. Medication errors may occur in association with administration of a different drug, property or administration route of the investigational product, or dosage or number of doses specified in the protocol.

The following procedure shall be followed:

The investigator or subinvestigator will report any medication error with TAS-205 that occurs, regardless of the onset of adverse events (even if the definition of a serious adverse event is not met), to the sponsor promptly.

## 12.7.3 Misuse

In this study, misuse is defined as any intended misuse of the investigational product (including abuse and use of more than the right dose) that increase risks. Any intended administration of the investigational product to subjects for whom the product is contraindicated will also be included. Any misuse found by the investigator or subinvestigator will be reported to the sponsor promptly.

## 12.7.4 Drug Interaction

In this study, drug interaction is defined as any interaction that occurs between the investigational product and concomitant medications affecting the pharmacokinetic profile and/or efficacy/adverse drug reactions, meals, or lifestyle habits (e.g., smoking, alcohol intake), etc. Any drug interaction found by the investigator or subinvestigator will be reported to the sponsor promptly.

# 13. Statistical Analysis

Statistical analysis will be performed in accordance to the plan described below. Details be specified in a separately prepared Statistical Analysis Plan.

# 13.1 Analysis Plan

# **13.1.1** Timing of Statistical Analysis

Statistical analyses will be performed after all subjects have completed the study.

# 13.1.2 Analysis Sets and Criteria for Handling Subject Data

# 13.1.2.1 Analysis Sets

The analysis sets in this study are defined as below.

Analysis set	Definition
Enrolled subjects	All subjects enrolled in the study
Subjects administered the	All enrolled subjects who received at least 1 dose of the investigational
investigational product	product
Full Analysis Set	All subjects administered the investigational product who were evaluated
(FAS)	for at least 1 efficacy endpoint (regardless of whether primary or
	secondary endpoint) after initiation of investigational product
	administration
Per Protocol Set	All subjects in the FAS, excluding those who met any of the following
(PPS)	conditions:
	• Subjects who were found to fail to meet any of the inclusion criteria after
	enrollment
	• Subjects who were found to meet any of the exclusion criteria after
	enrollment
	• Subjects who did not receive sufficient doses of the investigational
	product (administration rate at Week 24 < 70%)
	Subjects who used prohibited concomitant medications/therapies
	• Subjects who failed to comply with the dosage regimen of restricted
	concomitant medications
	• Subjects who were not evaluated for the primary endpoint

Table	13.1.2-	1 Definition	of Analysis	s Sets
ruore	1.2.1.2	Donninon	OI I muly bit	

If there is any subject for whom there are problems in determination of inclusion in the analysis sets, the handling of such subject will be determined through discussion between the sponsor and the medical expert before data lock.

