### 4.3 Discontinuation Criteria for Individual Subjects

Subjects who meet any of the following conditions will be withdrawn from investigational product administration:
- An adverse event that, in the opinion of the investigator, requires discontinuation of investigational product administration occurs.
- The subject or his legal representative requests to discontinue participation in the study (investigational product administration) (e.g., withdrawal of consent).
- There is a significant deviation from the study procedures.
- The subject cannot remain in the study because of residence change, hospital change, commitment to other tasks, etc.
- The subject requires persistent use of mechanical ventilation.
- The subject must use walking aids during the efficacy evaluations, including that of motor function.
- The dose was suspended for more than a total of 50 days during the specified administration period (missed dose\*1 will also be included; missed dose in a morning or evening will be counted as 0.5 days of dose suspension).

\*1 Only the missed dose of all tablets per dose will be counted.

• The investigator deems it necessary to discontinue the subject from the study for any other reason.

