# 7.4 Concomitant Medication/Therapy

# 7.4.1 Prohibited Concomitant Medications/Therapies

The concomitant medications/therapies specified below will be prohibited during the study period. The rationale is described in Section 14.6.

- Immunosuppressive medications (other than corticosteroids for DMD treatment)
- Persistent use of COX-1 and COX-2 inhibitors (excluding acetaminophen or other drugs that primarily centrally inhibit COX-3) and NSAIDs (temporary use for as-needed or other purpose is permissible)
- Other investigational product/therapy under study (medical device under development, etc.)
- Persistent use of mechanical ventilation (excluding non-persistent use or use while sleeping)

- Use of walking aids other than plantar orthosis (ankle foot orthosis, knee ankle foot orthosis, walker, etc.) in the 6MWD test and other motor function evaluations (use of wheelchair in daily activities is permissible)
- Rehabilitation proposed as a new program that obviously affects the present study (general or daily rehabilitation is permissible)
- Medications continuously used obviously for the improvement of the deterioration of physical function
- Sedatives used for skeletal muscle CT

The following concomitant medications (including temporary use for as-needed or other purpose) or therapies will be completely prohibited during 7 days before the motor function test:

- COX-1 and COX-2 inhibitors and NSAIDs
- Motor function test in another clinical research or trial

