## 10.3 Investigations for Individual Subjects at Discontinuation

If a subject is discontinued from the study as specified in Section 4.3, "Discontinuation Criteria for Individual Subjects," the investigator or subinvestigator will take appropriate measures as needed and perform clinical assessments specified for Day 169 (immediately after the end of the administration period) or follow-up test (discontinuation during the follow-up period) (clinical assessments for the safety endpoints) whenever possible. Any adverse event will be followed up whenever possible, as specified in Section 12.1.7, "Follow-up of Adverse Events."

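### The per protocol rule on prohibited therapies can remove a boy from the primary analysis because he got worse, or because of one NSAID dose before Week 12

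*Protocol*

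**What the plan says.** Protocol 13.1.3.2 and SAP 5 define the primary analysis as summary statistics by arm for the Week 24 change in 6MWD in the PPS. The same summary in the FAS is a sensitivity analysis; SAP 3.4.6 calls FAS analyses supplementary.

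Protocol Table 13.1.2-1 and SAP Table 4.1 exclude from the PPS "Subjects who used prohibited concomitant medications/therapies". A separate bullet excludes boys with no evaluation of the primary endpoint.

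Protocol 7.4.1 is the list that the first bullet points to. It includes:
- "Use of walking aids other than plantar orthosis (ankle foot orthosis, knee ankle foot orthosis, walker, etc.) in the 6MWD test" and the other motor function evaluations;
- persistent mechanical ventilation, with sleep-time and non-persistent use allowed;
- "Medications continuously used obviously for the improvement of the deterioration of physical function";
- COX-1/COX-2 inhibitors and NSAIDs, which even for as-needed use "will be completely prohibited during 7 days before the motor function test".

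Protocol 4.3 makes two of these events grounds for withdrawal from treatment as well: "The subject must use walking aids during the efficacy evaluations, including that of motor function" and "The subject requires persistent use of mechanical ventilation". After withdrawal, Protocol 10.3 and Table 1 note 16 call for safety assessments only.

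**The concern.** A per protocol exclusion is meant to remove data spoiled by departures from the protocol. Needing a walker or an ankle-foot orthosis in a motor test, or needing persistent ventilation, can instead be the disease advancing. The bullet does not separate the two. Selection into the primary set can then depend on how a boy fared after randomisation, and the arm with more such boys looks better than it is. If the drug keeps boys walking unaided, the losses fall mainly on placebo and the benefit is understated.

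The NSAID clause raises a different problem. The 7-day ban applies before every motor test, and motor tests are also done at Week 12. Read literally, one dose before Week 12 costs a boy his place in the primary analysis of a change that uses only baseline and Week 24. Protocol 16.2 is milder: it treats prohibited therapy as a significant deviation only when safety is definitely endangered.

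Protocol 14.1 says that efficacy will be read from numerical trends, and no test or interval accompanies the primary summary. The arm means therefore carry the interpretation.

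**Working it through.** **Step 1. Which boys the bullet decides.** Protocol 11.2 puts the 6MWD before the floor-rise, Timed Up & Go and 10-m tests. Protocol 7 puts the last dose after breakfast on the Week 24 evaluation day, so withdrawal from treatment no longer matters once that day's tests begin.

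| Event | PPS now | FAS Week 24 summary | Does editing the bullet help? |
|---|---|---|---|
| Needs an aid, or persistent ventilation, before Week 24 | Out; he also has no planned Week 24 6MWD | No value unless imputed | No |
| Unaided 6MWD at Week 24, aid used in a later test that day | Out through this bullet alone | In | Yes |
| Aid used in the Week 24 6MWD itself | Out | In if a distance is recorded; the protocol and SAP give no scoring rule | Yes, with a scoring rule |
| NSAID within 7 days before Week 12 only | Out through this bullet alone | In | Yes |
| NSAID within 7 days before the baseline or Week 24 test | Out | In | Left unchanged |

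**Step 2. What the FAS recovers.** SAP 3.4.2 imputes nothing by default, so the boy in the first row is missing from both Week 24 summaries. LOCF (SAP 8.3) can return him in the FAS, but with a value from before the loss; if baseline is carried forward he counts as 0 m change. LOCF does not return him to the PPS, because the bullet on unevaluated primary endpoints has already removed him.

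**Step 3. Size.** The documents give 33 boys, 3 x 11, chosen on feasibility. They give no SD, effect size or event rate, so there is no stated figure to reproduce and what follows is illustration. If k of 11 boys are removed and each is d metres worse than the mean of the rest, then

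upward shift in the arm mean = k x d / 11.

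- *Assumed values: ten boys at -20 m and one at -100, -200 or -300 m.* The full-arm mean is (10 x (-20) - 100)/11 = -27.3 m, (-200 - 200)/11 = -36.4 m or (-200 - 300)/11 = -45.5 m. Without him it is -20 m. The shifts are 7.3, 16.4 and 25.5 m.
- *Assumed values: others average 0 m and the removed boy loses his whole baseline distance, taken as 75 m (entry limit, Protocol 4.1) or 350 m (subgroup cut, SAP 6.1).* 75/11 = 6.8 m; 350/11 = 31.8 m. Two such boys: 13.6 and 63.6 m.
- *Milder decline, d = 25 to 100 m.* 25/11 = 2.3 m; 100/11 = 9.1 m.

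**Step 4. Between arms.** The distortion is (fraction removed on placebo - fraction removed on active) x d. With assumed fractions of 20% and 10% and d of 75 to 350 m, it is 0.10 x 75 = 7.5 m to 0.10 x 350 = 35 m, against the drug. Equal fractions with equal d give 0.

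The complete-loss figures are probably upper values for this bullet, since a boy who has lost walking is likely to have been withdrawn already. The NSAID route is not shown to depend on outcome. Its certain cost is numbers: each boy is 1/11 = 9.1% of his arm.

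**The case against.** A reader might infer that an effect on keeping boys walking unaided could not be seen at all. The documents do not support that. The primary summary is repeated in the FAS, the t-tests and MMRM run in both sets (Protocol 13.1.3.2, SAP 6.1), exclusions are listed with reasons, and reasons for discontinuation are summarised (SAP 6.4). Uneven loss could be found by someone who looked for it.

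A reader might also infer that editing the bullet keeps every decliner in the primary set. It does not. Protocol 4.3 and 10.3 remove those who decline before Week 24 by another route. This is the strongest objection, and it stands as a limit on the fix.

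Nor is the prohibited list unbounded. Aids count only in motor tests, and plantar orthoses, daily wheelchair use, sleep-time ventilation and as-needed NSAIDs outside the 7-day window are allowed. Persistent ventilation should be rare, given entry limits of 75 m for 6MWD and 50% of predicted for FVC. Doubtful cases go to the sponsor and medical expert before data lock, but a boy who used a walker in a motor test meets the bullet plainly and is not a doubtful case.

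Finally, Week 12 6MWD is a secondary endpoint and enters the PPS MMRM, so keeping affected Week 12 data out of the PPS is defensible. That justifies dropping the Week 12 value, not the boy's Week 24 change. An aided distance is indeed not comparable with an unaided one, but that calls for a scoring rule rather than deletion.

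**Conclusion.** The concern holds in a limited form. For boys who have a Week 24 6MWD, the prohibited-therapy bullet lets progression, or an NSAID dose that touches neither baseline nor Week 24, decide membership of the primary analysis set. The FAS offsets this in part: it keeps these boys, but it is ranked below the PPS and has no unimputed Week 24 value for boys withdrawn earlier.

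One excluded decliner moves an 11-boy arm's mean by about 7 to 25 m if the other ten average -20 m and he changes by -100 to -300 m. Milder decline gives 2 to 9 m. These are single-arm illustrations on assumed values. The direction of any between-arm bias depends on which arm loses more boys, and the documents do not say. A reader should not conclude that the plan favours the drug.

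This should be fixed, but it does not undermine the trial: the study is exploratory, the primary analysis is descriptive, and no type I error claim rests on it.

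**What to change.** Before code breaking, amend Protocol Table 13.1.2-1 and SAP Table 4.1 together:

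1. Remove motor-test walking-aid use and persistent ventilation from the prohibited-therapy exclusion, so that neither takes a boy with a Week 24 6MWD out of the primary set. Other prohibited medicines and therapies stay in the exclusion.
2. Prespecify how a Week 24 6MWD that could not be completed unaided is scored, for example as the distance covered before an aid was needed.
3. Apply the 7-day NSAID exclusion to the Week 24 change only when the affected test is baseline or Week 24. When it is Week 12, set only the Week 12 value to missing in the PPS Week 12 and MMRM analyses.
4. Present the FAS summary as co-equal with the PPS summary, with boys lacking a Week 24 6MWD counted by arm and reason.
5. State that these edits do not recover boys withdrawn before Week 24.

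No change to the withdrawal criteria is proposed. The cost is wording in two tables, one scoring rule and a count by arm. The downside is a slightly less strict PPS.
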